Objective 2: Baseline measures include patient demographics (sex, race/ethnicity, insurance coverage, rural/urban distribution), A1c control (mean A1c, % of patients with A1c >9%) and blood pressure. Clinics will also report number of DSMES referrals and DSMES attendance from the 9-month baseline period. In addition to baseline data, control and intervention clinics will generate monthly reports from their electronic health record system to track DSMES referrals and A1c control. DSMES attendance will also be reported by the clinics based on feedback data from the bidirectional referral system linking clinics with DSMES providers. All data will be examined at the clinic level and will be de-identified/aggregated to the clinic level prior to being shared with our study team. The following data is being extracted from patient electronic health records by clinic staff: DSMES referrals (% referred/% eligible at the clinic level), DSMES attendance (% attended/% referred at the clinic level), A1c Data (mean A1c levels and % with A1c >9% at the following time points will be extracted from electronic health record data and de-identified/aggregated into intervention vs control clinics as well as for the subset of patients within intervention vs control clinics that attended DSMES: baseline, monthly during the intervention and for the 6 months following intervention. In addition to the data being extracted from patients' electronic health records, we will also be receiving data from the DSMES providers on patient satisfaction with the class and diabetes knowledge. This outcome will be reported to the study team monthly for all patients from study clinics who attended DSMES classes during the 9-month study + 6 month follow-up period. Patient satisfaction and diabetes knowledge will be evaluated using de-identified data from patient surveys that are routinely collected by DSMES providers for all individuals immediately following DSMES attendance. KDPH will provide the study team with de-identified data for all patients from the two participating healthcare systems who attend DSMES (aggregated to the clinic level). All data used in Objective 2 is data that is routinely collected; no additional data will be collected as a part of the study.

Objective 3: We will use the same qualitative methods described in Objective 1 to analyze PRISM concepts, such as fidelity to the core components of the PFC and any necessary adaptations to either the PFC or to the selected implementation strategies (using the PRISM Assessment Tool, attached). To do so, we will conduct midpoint evaluations with program staff and other key stakeholders six months after initial program rollout as well as immediately upon conclusion. We will again use the PRISM survey and interview guide (see attachments: PRISM Assessment Tool and PRISM Interview Guide) to assess PRISM domains and provide context to understand the reasoning for any differences that exist between pre-implementation (i.e., anticipated) and midstream (i.e., unanticipated) adaptations. Two implementation scientists (Drs. [name] and [name]) with significant qualitative research experience will independently code the data and map responses to PRISM domains. To better understand the context and reasoning for implementation strategies, we will collect monthly reports from the learning collaborative teams; following the recommendations of Proctor and colleagues, we will ask the teams to (1) name, (2) define, and (3) operationalize (actor, action, target, temporality, dose, intended implementation outcome affected, and justification) each implementation strategy using a simple template document. These reports will help contextualize qualitative findings with respect to program adaptations. Finally, upon program conclusion, we will assess the implementation outcomes of feasibility, acceptability, and appropriateness on each implementation strategy as well as the intervention itself. To do so, we will ask program staff and other key stakeholders to complete a brief, 12-item psychometrically validated survey consisting of three scales measuring feasibility, acceptability, and appropriateness; for each scale, scores are summed and averaged for each individual scale, with higher scores indicating more favorable implementation outcomes (Attached: Triple P System Implementation Outcomes). These data will provide summative information about which strategies were effective at increasing DSMES utilization within the specific program setting. Taken together, these data will help refine any additional necessary adaptations and selection/refinement of implementation strategies for future scale-up activities.

Attachments

Data Collection & Research Materials

In this section, please provide the following:

- Describe all sources or methods for obtaining research materials about or from living individuals (such as specimens, records, surveys, interviews, participant observation, etc.), and explain why this information is needed to conduct the study.
- For each source or method described, please list or attach all data to be collected (such as genetic information, interview scripts,

survey tools, data collection forms for existing data, etc.).

- If you will conduct a record or chart review, list the beginning and end dates of the records you will view.

Please see attached file 'Data Collection Summary_UP FOR IT.pdf' for a complete list of data to be collected and surveys/tools for the full list of questions.

Attachments

Attach Type	File Name
DataCollection	PRISM assessment tool.pdf
DataCollection	PRISM Interview Guide.pdf
DataCollection	AIM_IAM_FIM_Implementation Outcomes.pdf
DataCollection	Data Collection Summary_UP FOR IT (Clean).pdf
DataCollection	Data Collection Summary_UP FOR IT (Highlighted).pdf
DataCollection	Interview Guide for Clinic Participants_080922.pdf
DataCollection	Interview Guide for KY REC_080922.pdf
DataCollection	Interview Guide for HLWD_081822_AKD.pdf

Resources

Describe the availability of the resources and adequacy of the facilities that you will use to perform the research. Such resources may include:

- Staffing and personnel, in terms of availability, number, expertise, and experience;
- Computer or other technological resources, mobile or otherwise, required or created during the conduct of the research;
- Psychological, social, or medical services, including equipment needed to protect subjects, medical monitoring, ancillary care, or counseling or social support services that may be required because of research participation;
- Resources for communication with subjects, such as language translation/interpretation services.

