Objective 2: The study population for Objective 2 is clinic staff from all clinics participating in UP FOR IT. Our partners at the Kentucky Regional Extension Cooperative have identified partner clinics in two healthcare systems in Kentucky (Big Sandy and Penny Royal, see LOS). We anticipate having between 5-6 participants at each of the 11 clinics that are participating in the intervention. This will yield a total sample size for Objective 2 of n=65 clinic staff. There are no additional inclusion/exclusion criteria beyond employment at a participating clinic. The proposed start date for enrolling these participants is October 1, 2022 and the proposed end date is November 30, 2022.

Objective 3: We will recruit key informants from two stakeholder groups: 1) clinic staff and clinicians who participated in the UP FOR IT intervention and 2) KDPH DSMES providers whose DSMES service catchment area included those clinical practices participating in UP FOR IT. Kentucky Regional Extension Cooperative staff will recruit two stakeholders from each of the 11 participating clinical practices from two healthcare systems (N=22) for surveys/key informant interviews. KDPH will aid in recruiting two DSMES providers from the regions where UP FOR IT took place. This will yield a total sample size for Objective 3 of 13 (n=22 clinic staff and n=2 DSMES providers). There are no additional inclusion/exclusion criteria beyond participation in UP FOR IT. The proposed start date for enrolling these participants is October 1, 2024 and the proposed end date is December 1, 2024.

Attachments

Indicate the targeted/planned enrollment of the following members of minority groups and their subpopulations. Possible demographic sources: [Census Regional Analyst Edition](#), [Kentucky Race/Ethnic Table](#), [Kentucky Population Data](#).

(Please note: The IRB will expect this information to be reported at Continuation Review time for Pre-2019 FDA-regulated Expedited review and Full review applications):

Participant Demographics

Cisgender Man 	Cisgender Woman 	TGNB/TGE 	Unknown/Not Reported
---	---	--	----------------------

American Indian/Alaskan Native:			
Asian:			
Black/African American:			
Latinx:			

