Objective 2 is a pragmatic cluster randomized trial. We have partnered with two rural healthcare systems (one in eastern Kentucky and one in Western Kentucky) for this study. Two clinics from each system will be randomized to participate in the intervention (4 total intervention sites) and the remaining clinics will serve as the control sites. The intervention consists of health information technology (including an automated patient identification system and bidirectional e-referral system connecting clinics to the DSMES providers) and a practice facilitation collaborative. The collaborative is a structured, facilitated process that brings together teams from different organizations to learn from one another. The collaborative utilizes the Model for Improvement, a quality improvement approach designed by the Institute for Healthcare Improvement that uses rapid cycle quality improvement – repeated PDSA (plan do study act) cycles meant to identify care quality barriers and rapidly implement and measure change. Teams from intervention clinics will apply this quality improvement strategy to identify and address quality gaps in diabetes care and DSMES utilization at their clinics. Practice facilitators on the study team will provide individualized coaching (practice facilitation) to clinics in the intervention arm of the study. We will assess the effect of the interventions on DSMES referrals (primary outcome), by comparing rates of referrals between intervention and control clinics (clinics within the healthcare system not randomized to the intervention). Secondary outcomes include DSMES attendance, patient satisfaction and diabetes knowledge, A1c control, and intervention feasibility and acceptability.

Objective 3 involves surveys and interviews with clinic staff that participated in the intervention and DSMES providers from the geographic areas where the intervention took place. Interviews will be conducted via phone and audio will be recorded. The goal of Objective 3 is to understand how the various implementation strategies embedded within the practice facilitation collaborative and clinical context influenced DSMES uptake to inform future refinement for program replication and scale-up.

Attachments

Subject Recruitment Methods & Advertising

Describe how the study team will identify and recruit subjects. Please consider the following items and provide additional information as needed so that the IRB can follow each step of the recruitment process.

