- How will the study team identify potential participants?
- Who will first contact the potential subjects, and how?
- Will you use advertisements? If so, how will you distribute those?
- How and where will the research team meet with potential participants?
- If applicable, describe proposed outreach programs for recruiting women, minorities, or disparate populations.
- How you will minimize undue influence in recruitment?
- Attach copies of all recruiting and advertising materials (emails, verbal scripts, flyers, posts, messages, etc.).

For additional information on recruiting and advertising:

- [IRB Application Instructions - Advertisements](#)
- [PI Guide to Identification and Recruitment of Human Subjects for Research](#)

Objective 1: Kentucky Regional Extension Cooperative staff who supported the first Diabetes Learning Collaborative will recruit two stakeholders from each of the five participating clinical practices to participate in surveys and a key informant interview. KDPH will aid in recruiting three DSMES providers from the regions where the first Diabetes Learning Collaborative took place. Recruitment phone and email scripts are attached.

Objective 2: We have partnered with two healthcare organizations in Kentucky for this pilot study: Mercy Health (Mercy Health Marcum & Wallace and Mercy Health Primary Care Clinics (see LOS) and Pikeville Medical Center (see LOS). Both healthcare organizations are non-profit health centers that provide primary and preventive health care to underserved patients. Pikeville includes one participating clinic that is a federally qualified health center. Recruitment for the proposed study targets healthcare organizations in rural settings with multiple clinical sites to allow control and intervention clusters to be randomized at the clinic level within a healthcare organization. This strategy enables us to pilot our intervention in two distinct rural Kentucky settings where the population is disproportionately burdened with diabetes. We will use as control sites other clinics within the healthcare organization with similar patient populations and are of a similar size, location, and financial structure as the intervention site.

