1. Expected risks: This study presents minimum risk to participants; that is the risk is not greater than what is experienced in everyday life. The study participants are employees of healthcare clinics who will participate in intervention. There is the potential for primary participants to experience frustration due to team dynamics and/or lack of improvement in clinical diabetes care goals. The risk of frustration is described in the consent form. To minimize this risk, participant teams receive training on positive team interactions.
 2. Primary participants in the study will not be prospectively evaluated for adverse events; however, they will be encouraged to contact the study PI if they feel they have experienced an adverse event.

B. Adverse event reporting

1. Every adverse event that is reported to the principal investigator by a participant will be documented.
2. An adverse event report will be generated for each event that will include a description of the event, when and how it was reported, and a determination of attribution.
3. Recipients of the report will include the study Safety Officer (healthcare research professional not part of the study), an institutional IRB official, and the NIDDK program official.
4. Adverse events will be reported quarterly.
5. Any action resulting in a temporary or permanent suspension of this study will be immediately reported to the appropriate NIDDK program official.

III. Safety Review Plan and Monitoring

A. Sample size justification: This pragmatic cluster randomized pilot study seeks to measure the feasibility, acceptability and approximate magnitude of effectiveness of the DSMES utilization interventions; thus, four clinics will be randomized to receive the intervention and the remaining seven clinics in the two participating rural healthcare systems will serve as controls.

B. Safety and study progress reviews

1. The two principal investigators will review adverse events with the study Safety Officer quarterly given the unmasked, low risk nature of the study.
2. The two principal investigators will review study progress (e.g., recruitment, retention, protocol adherence) quarterly.
3. The annual report will include: 1) list and summary of adverse events; 2) summary of recruitment and retention and reason for dropouts; 3) whether the study is on track to be completed and accomplish the stated aims.

C. There are no Stopping Rules.**IV. Informed Consent**

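### The 9-month baseline referral data enter neither the clinic draw nor the stated primary comparison; with 4 versus 7 clinics, the comparison should be adjusted for them

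*Combined protocol and SAP*

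**What the plan says.** - **Draw.** Study Design, Objective 2: "Two clinics from each system will be randomized to participate in the intervention (4 total intervention sites"). The sample size paragraph of the Data and Safety Monitoring Plan (III.A) agrees: "four clinics will be randomized to receive the intervention and the remaining seven clinics" serve as controls. System is the only stratification factor.
- **Outcome and comparison.** Research Procedures, Objective 2, gives the outcome as "DSMES referrals (% referred/% eligible at the clinic level"). Study Design describes the analysis as "by comparing rates of referrals between intervention and control clinics", and the Records, Privacy, and Confidentiality section repeats this. Neither place gives a model, a covariate or a change from baseline.
- **Baseline.** Research Procedures, Objective 2: "Clinics will also report number of DSMES referrals and DSMES attendance from the 9-month baseline period". No use of these data is stated. The eligible denominator appears with the outcome definition but not with the baseline item.
- **Comparability.** Subject Recruitment, Objective 2, describes controls as resembling intervention clinics in patients, size, location and finances. Referral rate is not on that list.
- **Purpose.** The pilot is to measure, among other things, the "approximate magnitude of effectiveness of the DSMES utilization interventions", and it feeds a planned larger study.

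**The concern.** How often a clinic referred before the trial is the obvious predictor of how often it refers afterwards. With four intervention clinics, one habitually high-referring clinic is a quarter of the arm. The plan collects the information needed to deal with this but gives it no role in allocation or analysis.

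The similarity wording in the recruitment section does not fill the gap. All clinics not drawn become controls, so none is selected for similarity. The clinics also differ in type: "Pikeville includes one participating clinic that is a federally qualified health center".

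At stake is the precision of the effect estimate that will inform the planned study, and how a reader can interpret a difference between arms that may already have existed at baseline.

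**Working it through.** The documents give no power, SD or imbalance figure, so there is nothing of the plan's own to reproduce. The clinic counts agree: 2 × 2 = 4, and 4 + 7 = 11.

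**Inputs.** From the documents: two clinics drawn per system, 11 clinics in all. Assumed: between-clinic SD within system = 1 (all results are in that unit), normal clinic rates, and a baseline-to-follow-up correlation ρ of 0.8 or 0.5. Clinics per system are not given. The splits 5/6, 4/7 and 3/8 are the only ones that leave at least one control in each system.

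**1. Chance imbalance at baseline.** In a system with n clinics, the difference in means has variance 1/2 + 1/(n−2). With the two systems weighted equally, SE = √[(v₁+v₂)/4]. With inverse-variance weights, SE = √[1/(1/v₁+1/v₂)]. Then P(|d|>t) = 2[1−Φ(t/SE)].

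| Split | v₁, v₂ | SE equal / inverse-variance | P(>0.5 SD), equal weights | P(>0.8 SD) | P(>1 SD) |
|---|---|---|---|---|---|
| 5/6 | 0.833, 0.750 | 0.629 / 0.628 | 43% | 20% | 11% |
| 4/7 | 1.000, 0.700 | 0.652 / 0.642 | 44% | 22% | 13% |
| 3/8 | 1.500, 0.667 | 0.736 / 0.679 | 50% | 28% | 17% |

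Ignoring system, SE = √(1/4+1/7) = 0.627 and P(>0.5 SD) = 42.5%.

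**2. Effect on an unadjusted estimate.** Given an imbalance d, the expected shift is ρ × d. For d = 0.5 SD this is 0.40 SD at ρ = 0.8 and 0.25 SD at ρ = 0.5. Averaged over draws it is zero.

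**3. Gain from adjustment, with the slope estimated.** After intercept, system and arm, 11 − 3 = 8 degrees of freedom remain. Estimating a slope multiplies the variance by 1 + 1/(8−2) = 7/6 on average. So SD(adjusted) = SE × √(1−ρ²) × √(7/6), with the inverse-variance SE as the unadjusted value.

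| Split | Unadjusted | ρ = 0.8 | ρ = 0.5 | ρ = 0 |
|---|---|---|---|---|
| 5/6 | 0.63 | 0.41 | 0.59 | 0.68 |
| 4/7 | 0.64 | 0.42 | 0.60 | 0.69 |
| 3/8 | 0.68 | 0.44 | 0.64 | 0.73 |

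Break-even is at 1−ρ² = 6/7, so ρ = √(1/7) = 0.38. Simulation of least-squares fits with system, arm and baseline agrees with this table.

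**4. Constraining the draw instead.** There are C(n₁,2) × C(n₂,2) = 150, 126 or 84 allocations. Drawing from the half best balanced on the pooled within-system difference in baseline referral rate alone leaves 75, 63 or 42. In simulation (4,000 data sets) the root-mean-square imbalance falls from 0.63–0.74 to 0.26–0.35 SD, and P(>0.5 SD) to about 4–15%.

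**The case against.** **The design is legitimate.** Stratified random allocation is a reasonable choice for a pilot that asks only for an approximate magnitude, and the mean error is zero under every scheme considered. A chance imbalance is part of the ordinary sampling error of a 4-versus-7 comparison. This stands. A reader might infer that the draw biases the estimate, or that a large imbalance is an even bet. The documents and arithmetic support neither: the near-even figure belongs to the 0.5 SD threshold, and beyond 1 SD the chance is 11–17%.

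**Silence is not refusal.** A reader might also infer that the investigators decided against using the baseline. The text only omits it. A data collection summary is listed as an attachment but not reproduced, so it could not be checked.

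**Practical size is unknown.** No between-clinic SD, baseline rate or persistence is given. If the SD were 5–10 percentage points (an assumption), 0.5 SD would be 2.5–5 points. That is modest beside the rise from 0% to 31% cited in Background from another project, but not beside a small effect. This stands too.

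**Balancing at the draw may promise too much.** It is tempting to think that balancing on several clinic features would almost remove the problem. Scoring each system's difference on two independent features still leaves a 29–39% chance of a referral imbalance above 0.5 SD. The number of patients with diabetes, a natural second feature, is not among the listed baseline measures.

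**The draw has probably happened.** The protocol change log shows the open-to-enrolment answer changed from yes to no in December 2024. This does not date the randomisation, but it makes the analysis remedy the more useful one.

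**Conclusion.** The point holds as a gap in the stated analysis, not as a fault in randomising. The plan collects nine months of baseline referrals and gives them no stated role. The unadjusted comparison is unbiased on average. It nevertheless has a 43–50% chance of starting from a baseline gap above half a between-clinic SD, and a 20–28% chance of one above 0.8 SD.

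What adjustment buys depends on how persistent clinic referral habits are, which the documents do not say. The SD of the estimate falls by about a third at ρ = 0.8, the gain is slight at ρ = 0.5, and there is a loss of about 0.05 SD at ρ = 0. All figures rest on normal clinic rates, a common SD and the three assumed splits. The size in percentage points cannot be fixed from the documents.

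**What to change.** **Primary change.** In Study Design (Objective 2) and in the matching sentence under Records, Privacy, and Confidentiality, state that the primary comparison is a clinic-level analysis of referral rate, adjusted for system and for each clinic's 9-month baseline referral rate. Define the baseline rate with the same eligible-patient denominator as follow-up, and report baseline rates by arm. State the number of clinics per system; Subject Demographics and Subject Recruitment name different partner systems, and these should be reconciled.

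**Cost.** One degree of freedom (8 to 7), and a small precision loss, up to about 0.06 SD, if the correlation is below about 0.3–0.4. Referral counts are already planned. The baseline eligible count is not explicitly listed and may be one added figure per clinic. The monitoring plan (V.A) describes validation of record reporting for intervention clinics only, so control-clinic baseline data need the same check.

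**Only if clinics are not yet allocated.** Extract the baseline for all 11 clinics first. Then draw at random from the half of allocations best balanced on the pooled within-system difference in baseline referral rate alone. Randomisation then waits for the extract, and any permutation test must be restricted to the retained allocations. The same approach would suit the planned larger study.

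### Clinics are randomised within two health systems, but the primary comparison of referral rates is not stated to be made within system

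*Combined protocol and SAP*

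**What the plan says.** Under Study Design, Objective 2 is a pragmatic cluster randomised trial in two rural systems, "one in eastern Kentucky and one in Western Kentucky". The allocation is "Two clinics from each system will be randomized to participate in the intervention (4 total intervention sites"), and all other clinics are controls. Subject Recruitment Methods confirms the level of randomisation: "control and intervention clusters to be randomized at the clinic level within a healthcare organization".

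The primary analysis is one sentence in Study Design: "We will assess the effect of the interventions on DSMES referrals (primary outcome), by comparing rates of referrals between intervention and control clinics". A bracket then defines the controls as "clinics within the healthcare system not randomized to the intervention". Records, Privacy, and Confidentiality repeats this and adds no method. Research Procedures defines the referral outcome as a clinic-level percentage and collects a nine-month baseline, but states no use of the baseline in the comparison.

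The sample size paragraph of the Data and Safety Monitoring Plan (III.A) gives four intervention and seven control clinics, without a split by system. The two systems are also not named consistently. Study Population refers to "partner clinics in two healthcare systems in Kentucky (Big Sandy and Penny Royal, see LOS"), while Subject Recruitment Methods says "We have partnered with two healthcare organizations in Kentucky for this pilot study: Mercy Health", with Pikeville Medical Center as the second organisation.

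**The concern.** When randomisation is stratified and the allocation ratio differs between strata, the arms hold different mixes of strata by design. Here the intervention arm is half from each system. An odd number of controls cannot be. The smaller system is therefore over-represented in the intervention arm, and a contrast that ignores system attributes part of any system difference to the intervention. The direction depends on which system is smaller: downward if the smaller one refers less, upward if it refers more. The system difference also stays in the residual variance, so the interval is wider than it need be.

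A difference between the systems is plausible. The protocol says the aim is to "pilot our intervention in two distinct rural Kentucky settings". The pilot is meant to give a rough size of the effect (III.A) and preliminary data for a planned R01 study (Objectives). A shifted or needlessly imprecise estimate would carry into that design.

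**Working it through.** **1. The plan's counts.** 2 systems × 2 clinics = 4 intervention; 11 − 4 = 7 controls. This agrees with III.A. The documents give no power, ICC, effect size or clinic size to reproduce.

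**2. Share of a system difference carried by the simple contrast.** Let k be the controls in the smaller system and D the system difference in mean referral rate (smaller minus larger). With no intervention effect, the expected contrast of clinic means is D × (2/4 − k/7) = D × (7 − 2k)/14.

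| Clinics | k | Share of D | Chance of intervention, by system | Shift, D = 4 points | Shift, D = 10 points |
|---|---|---|---|---|---|
| 5/6 | 3 | 1/14 = 0.071 | 2/5, 2/6 | 0.3 | 0.7 |
| 4/7 | 2 | 3/14 = 0.214 | 2/4, 2/7 | 0.9 | 2.1 |
| 3/8 | 1 | 5/14 = 0.357 | 2/3, 2/8 | 1.4 | 3.6 |

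These are the only splits of 11 that leave each system a control. No split gives zero, because 7 is odd. With a system term the share is 0 in every row.

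**3. Cost of the system term.** In units of the within-system clinic variance, the simple contrast has variance 1/4 + 1/7 = 0.3929. With a and b clinics per system, the adjusted one has 1/[2(a−2)/a + 2(b−2)/b] = 0.3947, 0.4118, 0.4615. The standard error ratios are 1.002, 1.024, 1.084. Going from 9 to 8 df multiplies by 2.306/2.262 = 1.019. The interval is therefore 1.022, 1.044 or 1.105 times as wide if the systems do not differ.

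**4. Break-even.** Assumptions, none from the documents: 300 eligible patients per clinic, mean referral 10%, ICC 0.05. Clinic variance is 0.10 × 0.90 × (0.05 + 0.95/300) = 0.00479, SD 0.0692. The term lowers root mean squared error once D exceeds SD × √(v_adjusted − v_simple)/share = 4.2, 4.4, 5.1 points. For ICC 0.02 to 0.10 the ranges are 2.8 to 5.8, 2.9 to 6.2 and 3.4 to 7.1.

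**5. Simulation with no effect** (same assumptions, 20,000 trials per scenario; order 5/6, 4/7, 3/8). Mean 95% interval widths, simple then adjusted:

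- Smaller system 5%, larger 15%: 0.243/0.194, 0.245/0.208, 0.241/0.230, so the term narrows the interval by 20%, 15%, 5%. Simple-contrast rejection is 0.012, 0.020, 0.045.
- Smaller system 15%, larger 5%: 0.236/0.182, 0.224/0.175, 0.205/0.173, so narrower by 23%, 22%, 16%. Simple-contrast rejection is 0.014, 0.029, 0.068.
- With the term, rejection is 0.041 to 0.052 throughout.
- Systems at 8% and 12%: the width changes by −3%, 0%, +7%, with no gain in root mean squared error.

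**6. Coverage under an assumed 20-point effect.** The adjusted equal-variance t interval covers 0.881 to 0.934. With a ten-point gap, adjusted against simple is 0.918/0.958, 0.927/0.950, 0.934/0.928 (smaller system lower) and 0.907/0.954, 0.893/0.932, 0.881/0.900 (smaller system higher). The adjusted interval covers less in five of the six cases.

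**7. Within-system permutation.** The allocations number C(5,2)×C(6,2) = 150, C(4,2)×C(7,2) = 126 and C(3,2)×C(8,2) = 84, so the smallest attainable p-values are about 0.007, 0.008 and 0.012. Rejection with no effect was 0.039 to 0.057 in 2,000 trials (Monte Carlo SE 0.005).

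**The case against.** The strongest reply is that the simple contrast is not in the documents. They say only that rates will be compared. The bracket on controls fits a within-system comparison, and so does the statement in Subject Recruitment Methods that controls come from the same organisation and resemble the intervention site in patients, size, location and finances. That stands as a limit: a reader might infer that the planned estimate is biased, and the text does not support this. But those sentences say which clinics are controls, not how the two systems are combined, so the choice is left open.

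Other objections also stand in part:

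- The fractions need exactly seven controls. The attachment list shows letters of support for one pair of systems from January 2022 and for the other from April 2023, so the count of 11 and the east/west description may belong to the earlier pair. An even number of controls could make the share zero.
- The fractions apply to unweighted clinic means. With patient-pooled rates and an assumed clinic-size coefficient of variation of 0.5, the share runs (5th to 95th percentile) from −0.18 to 0.33, −0.03 to 0.45 and 0.13 to 0.58.
- The shift is small against an interval half-width of about 10 to 12 points. The Background cites a project that began at 0% referral; rates near zero at baseline would leave little room for a system gap.
- A change-from-baseline comparison would remove a stable system difference. The data are collected, but no such analysis is stated.

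**Conclusion.** The point holds in a conditional form. Randomisation is within system, and the stated primary comparison does not say that the analysis is. If there are seven controls and a simple contrast of clinic means is used, it carries 1/14, 3/14 or 5/14 of any system difference. Under an assumed ten-point gap, its no-effect coverage runs from about 0.93 to 0.99, against about 0.95 to 0.96 with a system term. The consequence is minor at 5/6 or below a gap of about 4 to 5 points, and material only with an uneven split or a large gap.

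Two stronger readings should be resisted. One is that the trial will report a biased effect: neither the analysis nor the system gap is known. The other is that adding the system term improves everything: below the break-even it does not reduce error, and under a large effect its t interval can cover less than the simple one. The case for it is that it follows the randomisation at little cost. The ICC, clinic size, referral rates and effect size are all assumptions. The Data Collection Summary attachment was not available for this review.

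**What to change.** 1. Reconcile Study Population with Subject Recruitment Methods on which two systems take part, and state the number of clinics in each.
2. State the primary estimate as a within-system one: a clinic-level regression of referred/eligible on arm and health system (8 df with 11 clinics), or the equivalent stratified contrast, reported as a difference with its 95% interval.
3. Take the p-value from a permutation test that re-randomises two clinics within each system.
4. Say that the equal-variance t interval may under-cover if the intervention raises between-clinic variance (about 0.88 to 0.93 under an assumed 20-point effect).
5. Date the analysis text relative to the analysis of referral outcomes, or label it as set afterwards. The protocol change log shows enrolment being closed in December 2024.

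The cost is one degree of freedom: an interval about 2%, 4% or 10% wider (5/6, 4/7, 3/8) if the systems do not differ. No new data are needed for the primary estimate.

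Two sensitivity analyses are optional. An HC2 interval with Satterthwaite df covered 0.935 to 0.965 under the 20-point effect, at the price of a wider interval. A model that adds the baseline referral rate (7 df) needs the baseline eligible count from each clinic, and gains precision only if the baseline/follow-up correlation between clinics exceeds about 0.4 to 0.5.
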